6.8 Safety Analysis

The safety endpoints for this study are AEs, biomicroscopy findings, and device deficiencies.

All AEs occurring from the time a subject signs informed consent to study exit will be accounted for in the reporting. Descriptive summaries (frequencies and percentages) for ocular and nonocular AEs will be presented by Medical Dictionary for Regulatory Activities Preferred Terms. AEs leading to study discontinuation, significant nonserious AEs, and SAEs will be identified. Individual subject listings will be provided, as necessary.

Individual subject listings will be provided for AEs that occur after signing informed consent but prior to exposure to study lenses.

Each biomicroscopy parameter will be tabulated by its grade. For each applicable biomicroscopy parameter, frequencies and percentages of eyes that experience an increase of ≥ 2 grades from baseline (last assessment prior to study lens exposure) to any subsequent visit within the same period will be presented. A supportive listing will be generated which will include all biomicroscopy data from all visits within the same period for these eyes experiencing the increase.

Two listings (prior to exposure of study lenses and treatment-emergent) of device deficiencies, as recorded on the Device Deficiency Form, will be provided. Additionally, each device deficiency category will be tabulated.

No inferential testing will be done for safety analysis.

6.9 Interim Analyses

There are no plans to conduct an interim analysis, and no criteria by which the study would be terminated early based upon statistical determination.

6.10 Sample Size Justification

No formal sample size calculation is provided given the descriptive nature of the study

7 ADVERSE EVENTS AND DEVICE DEFICIENCIES

Terms and Definitions

Adverse Event (AE)	
Untoward medical occurrence, unintended disease or injury, or untoward clinical signs (including abnormal laboratory findings) in subjects, users or other persons, whether or not related to the investigational medical device or comparator and whether anticipated or unanticipated.
 
Note: For subjects, this definition includes events related to the investigational medical device, comparator, or the procedures involved. For users or other persons, this definition is restricted to the use of investigational medical devices or comparator.

--------------------	---

Adverse Device Effect (ADE)	
Adverse event related to the use of an investigational medical device or comparator
 
Note: This definition includes adverse events resulting from insufficient or inadequate instructions for use, deployment, implantation, installation, or operation; any malfunction; and use error or intentional misuse.

Anticipated Serious Adverse Device Effect (ASADE)	An effect which by its nature, incidence, severity, or outcome has been identified in the risk assessment.
Device Deficiency	
Inadequacy of a medical device with respect to its identity, quality, durability, reliability, usability, safety, or performance.
 
Note: This definition includes malfunctions, use errors, and inadequacy in the information supplied by the manufacturer including labelling related to the investigational medical device or the comparator.

Malfunction	Failure of an investigational medical device to perform in accordance with its intended purpose when used in accordance with the instructions for use or clinical investigation plan (CIP), or investigator's brochure (IB).
Nonserious Adverse Event	Adverse event that does not meet the criteria for a serious adverse event.
Serious Adverse Device Effect (SADE)	Adverse device effect that has resulted in any of the consequences characteristic of a serious adverse event.
Serious Adverse Event (SAE)	
Adverse event that led to any of the following:
 
• Death.• A serious deterioration in the health of the subject, users or other persons as defined by one or more of the following:
a) a life-threatening illness or injury
Note: Life-threatening means that the individual was at immediate risk of death from the event as it occurred, i.e., it

	
does not include an event which hypothetically might have caused death had it occurred in a more severe form.
 
b) any potentially sight-threatening event or permanent impairment to a body structure or a body function including chronic diseases.c) in-patient hospitalization or prolonged hospitalization.d) a medical or surgical intervention to prevent a) or b).e) any indirect harm as a consequence of incorrect diagnostic test results when used within manufacturer's instructions for use. 
• Fetal distress, fetal death, congenital abnormality, or birth defect including physical or mental impairment. 
Note: Planned hospitalization for a preexisting condition, or a procedure required by the CIP, without serious deterioration in health, is not considered a serious adverse event.
 
Refer to Section 7.1 for additional SAEs.

Serious Health Threat	
Signal from any adverse event or device deficiency that indicates an imminent risk of death or a serious deterioration in the health in subjects, users or other persons, and that requires prompt remedial action for other subjects, users or other persons
 
Note: This would include events that are of significant and unexpected nature such that they become alarming as a potential serious health hazard or possibility of multiple deaths occurring at short intervals.

Significant Nonserious Adverse Event	
A symptomatic, device-related, non-sight-threatening adverse event that warrants discontinuation of any contact lens wear for greater than or equal to 2 weeks.
 
Refer to Section 7.1 for additional Significant Nonserious AEs.

Unanticipated Serious Adverse	Serious adverse device effect which by its nature, incidence, severity, or outcome has not been identified in the risk assessment.

Device Effect (USADE)	
Use Error	
User action or lack of user action while using the medical device that leads to a different result than that intended by the manufacturer or expected by the user.
 
Note:
 
a) Use error includes the inability of the user to complete a task.b) Use errors can result from a mismatch between the characteristics of the user, user interface, task, or use environment.c) Users might be aware or unaware that a use error has occurred.d) An unexpected physiological response of the patient is not by itself considered a use error.e) A malfunction of a medical device that causes an unexpected result is not considered a use error.

7.1 General Information

An AE is any untoward medical occurrence, unintended disease or injury, or untoward clinical signs (including abnormal laboratory findings) in subjects, users, or other persons, whether or not related to the investigational medical device (*test product*). Refer to the Glossary of Terms and figures below for categories of AEs and SAEs.

Figure 7-1 Categorization of All AEs

[figure not shown]
[figure not shown]

Figure 7-2 Categorization of All Serious Adverse Events

Specific Events Relevant to this Protocol

Serious Adverse Events

In addition to reporting all AEs (serious and nonserious) meeting the definitions, the investigator must report any occurrence of the following as an SAE:

- An ocular infection including a presumed infectious ulcer with any of the following characteristics:
 - Central or paracentral location
 - Penetration of Bowman's membrane
 - Infiltrates > 2 mm diameter
 - Iritis
 - Increase in intraocular pressure
 - Culture positive for microorganisms
 - Increasing size or severity at subsequent visits
- Any central or paracentral corneal event (such as neovascularization) that results in permanent opacification
- Hypopyon
- Hyphema
- Neovascularization within the central 6 mm of the cornea
- Permanent vision loss as defined by loss of 2 or more lines of BCVA from enrollment visit that fails to resolve
- Uveitis (anterior, intermediate, or posterior)
- Corneal abrasion affecting \geq 50% of corneal surface area

Significant Nonserious Adverse Events

A significant nonserious AE is a symptomatic, device-related, non-sight-threatening AE that warrants discontinuation of any contact lens wear for greater than or equal to 2 weeks. In addition, the investigator must report any occurrence of the following as a Significant Nonserious AE:

- Peripheral nonprogressive noninfectious ulcers
- All symptomatic corneal infiltrative events
- Corneal staining score greater than or equal to Grade 3 (Refer to MOP for grading scales)
- Temporary vision loss as defined by loss of 2 or more lines of BCVA from enrollment visit that persists for 2 or more weeks

- Neovascularization score greater than or equal to Grade 2

The above events are based upon the categories provided in the ISO 11980 and the US FDA Premarket Notification (510(k)) Guidance Document for Daily Wear Contact Lenses

Device Deficiencies

A device deficiency is inadequacy of a medical device with respect to its identity, quality, durability, reliability, safety, or performance. A device deficiency may or may not be associated with patient harm (i.e., ADE or SADE); however, not all ADEs or SADEs are due to a device deficiency. The investigator should determine the applicable category listed in the Device Deficiency eCRF for the identified or suspect device deficiency and report any patient harm separately. Examples of device deficiencies include the following:

- Failure to meet product specifications (e.g., incorrect lens power/diameter/base curve/color)
- Lens/solution cloudy
- Lens surface/edge defect
- Torn lens during handling/in pack
- Packaging deficit (e.g., mislabeled product, tampered seal, leaking bottle/container)
- Suspect product contamination

7.2 Monitoring for Adverse Events

At each visit, after the subject has had the opportunity to spontaneously mention any problems, the investigator should inquire about AEs by asking the standard questions shown below and report as applicable:

- “Have you had any health problems since your last study visit?”
- “Have there been any changes in the medicines you take because of a new health issue since your last study visit?”

Additionally, changes in *any protocol-specific parameters and/or questionnaires* evaluated during the study are to be reviewed by the investigator. Any untoward (unfavorable and unintended) change in *a protocol-specific parameter or questionnaire response* that is clinically relevant, in the opinion of the investigator, is to be reported as an AE. These clinically relevant changes will be reported regardless of causality.

7.3 Procedures for Recording and Reporting

AEs are collected from the time of informed consent. Any preexisting medical conditions or signs/symptoms present in a subject prior to the start of the study (i.e., before informed consent is signed) are not considered AEs in the study and should be recorded in the Medical History section of the eCRF.

In addition, temporary lens awareness or visual changes during the fitting process are not considered AEs if the investigator assesses that the symptom(s) can reasonably resolve within the anticipated adaptation period.

For each recorded event, the ADEs and SAEs documentation must include: date of occurrence, severity, treatment (if applicable), outcome, and assessments of the seriousness and causality. In addition, the investigator must document all device deficiencies reported or observed with test and comparator products on the Device Deficiency eCRF. The site must submit all available information on ADEs, SAEs, and device deficiencies to the study sponsor immediately as follows:

- ADEs or SAEs are documented on the *Serious Adverse Event and Adverse Device Effect* eCRF within 24 hours of the investigator's or site's awareness.
- Device deficiencies are documented on the *Device Deficiency* eCRF within 24 hours of the investigator's or site's awareness.
- A printed copy of the completed *Serious Adverse Event and Adverse Device Effect* and/or *Device Deficiency* eCRF must be included with product returns.
- Additional relevant information after initial reporting must be entered into the eCRF as soon as the data become available.
- Document all relevant information from Discharge Summary, Autopsy Report, Certificate of Death, etc., if applicable, in narrative section of the *Serious Adverse Event and Adverse Device Effect* eCRF.

Note: Should the EDC system become nonoperational, the site must complete the appropriate paper *Serious Adverse Event and Adverse Device Effect* and/or *Device Deficiency* Form. The completed form is emailed to the study sponsor at [contact] according to the timelines outlined above; however, the reported information must be entered into the EDC system once it becomes operational.

Any AEs and device deficiencies for nonstudy marketed devices/products (i.e., CLEAR CARE Cleaning & Disinfecting Solution) will be considered and processed as spontaneous

(following the postmarket vigilance procedures) and should be communicated to the device's/product's manufacturer as per local requirements.

Study sponsor representatives may be contacted for any protocol-related question.

Further, depending upon the nature of the AE or device deficiency being reported, the study sponsor may request copies of applicable portions of the subject's medical records. The investigator must also report all AEs and device deficiencies that could have led to a SADE according to the requirements of regulatory authorities or IRB/IEC.

Intensity and Causality Assessments

Where appropriate, the investigator must assess the intensity (severity) of the AE based upon medical judgment with consideration of any subjective symptom(s), as defined below:

Intensity (Severity)

Mild	An AE is mild if the subject is aware of but can easily tolerate the sign or symptom.
Moderate	An AE is moderate if the sign or symptom results in discomfort significant enough to cause interference with the subject's usual activities.
Severe	An AE is severe if the sign or symptom is incapacitating and results in the subject's inability to work or engage in their usual activities.

For every AE in the study, the investigator must assess the causality (Related or Not Related to the medical device or study procedure). An assessment of causality will also be performed by study sponsor utilizing the same definitions, as shown below:

Causality

Related	An AE classified as related may be either definitely related or possibly related where a direct cause and effect relationship with the medical device or study procedure has not been demonstrated, but there is a reasonable possibility that the AE was caused by the medical device or study procedure.
Not Related	An AE classified as not related may either be definitely unrelated or simply unlikely to be related (i.e., there are other more likely causes for the AE).

The study sponsor will assess the AEs and may upgrade the investigator's assessment of seriousness and/or causality. The study sponsor will notify the investigator of any AEs that are upgraded from nonserious to serious or from unrelated to related.

7.4 Return product analysis

Alcon products associated with device deficiencies and/or product related AEs should be returned and must include the Complaint # which will be provided by study sponsor after the case is entered in the study sponsor's Global Product Complaint Management System. These products should be returned to the sponsor at the end of the study, unless instructed otherwise by the sponsor.

7.5 Follow-Up of Subjects with Adverse Events

The investigator is responsible for adequate and safe medical care of subjects during the study and for ensuring that appropriate medical care and relevant follow-up procedures are maintained after the study.

The investigator should provide the study sponsor with any new safety information (which includes new AEs and changes to previously reported AEs) that may affect the safety evaluation of the device. For AEs that are unresolved/ongoing at time of subject discontinuation or exit from study, any additional information received at follow-up should be documented in the eCRFs up to study completion (i.e., database lock).

Any additional data received up to 1 month after subject discontinuation or exit must be documented and available upon the study sponsor's request. All complaints received after this time period will be considered and processed as spontaneous and should be communicated to the medical device's manufacturer as per local requirements.

The investigator should also report complaints on non-Alcon products directly to the manufacturer as per the manufacturer's instructions or local regulatory requirements.

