	 Contralateral  Bilateral  Monocular lens wear	 Randomized
Test Product Details	Primary component/material	serafilcon A
	Product Name	Alcon serafilcon A contact lenses
	LID Number	LID022821
	Manufacturer	Alcon Laboratories, Inc. [name] USA
	Rx Power Range	-1.00 to -6.00 D in 0.25 steps
Comparator Product Details	Primary component/material	senofilcon A
	Product Name	Acuvue Oasys 2 Week with Hydraclear Plus (AOHP)
	LID Number	N/A
	Manufacturer	Johnson & Johnson
	Rx Power Range	-1.00 to -6.00 D in 0.25 steps
	Other	Base Curve: 8.4 mm and 8.8 mm
Inclusion Criteria	1. Subject must be at least 18 years of age.	

	
2. Subject must be able to understand and must sign an ICF that has been approved by an IRB.3. Successful wear of spherical soft contact lenses in both eyes for a minimum of 5 days per week and 8 hours per day during the past 3 months.4. Manifest cylinder of ≤ 0.75 D in each eye.5. BCVA 20/25 Snellen (0.10 logMAR) or better in each eye.6. Subject must be willing to stop wearing their habitual contact lenses for the duration of study participation.7. Able to wear contact lenses within a range of sphere power from -1.00 to -6.00 D (0.25 D steps) and subject willing and able to wear the study lenses for the full duration of the study.
	
9. Subject must be able to be successfully fit with test and comparator lenses.
Exclusion Criteria	
1. Any anterior segment infection, inflammation, or abnormality or disease (including systemic) that contraindicates contact lens wear, as determined by the investigator.2. Any use of systemic or ocular medications for which contact lens wear could be contraindicated, as determined by the investigator.3. History of refractive surgery or plan to have refractive surgery during the study or irregular cornea in either eye.4. Ocular or intraocular surgery (excluding placement of punctal plugs) within the previous 12 months or planned during the study.5. Biomicroscopy findings at screening that are moderate (Grade 3) or higher and/or corneal vascularization that is mild (Grade 2) or higher; presence of corneal infiltrates.

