8 CONFIDENTIALITY, BIAS, AND MASKING

8.1 Subject Confidentiality and Methods Used to Minimize Bias

The investigator must ensure that the subject's anonymity is maintained throughout the course of the study. In particular, the investigator must keep an enrollment log with confidential identifying information that corresponds to the subject numbers and initials of each study participant. All documents submitted to the sponsor will identify the subjects exclusively by number and demographic information. No other personally identifying information should be transmitted to the sponsor.

This study is double-masked with subjects randomized to use Alcon serafilcon A or AOHP contact lens for the duration of 2-week treatment period.

The investigator and sponsor personnel (other than site monitors, clinical operations lead, person responsible for generating the randomization schedule, and unmasked clinical data managers) involved in reporting, obtaining, and/or reviewing the clinical evaluations will be masked to the identity of the contact lens being administered. This level of masking will be maintained throughout the conduct of the study. Unmasking will occur only after all planned study data have been validated, and the database locked.

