8.2 Unmasking of the Study Treatment

Masked information on the identity of the assigned medical device should not be disclosed during the study. In the event of a medical emergency where the knowledge of subject treatment is required, individual investigator(s) will have the ability to unmask the treatment assignment for a specific subject. If time allows, the appropriate study sponsor representative should be contacted prior to unmasking. The study sponsor must be informed of all cases in which the code was broken and of the circumstances involved. Additionally, the study sponsor may be required to unmask the information in order to fulfill expedited regulatory reporting requirements.

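### Does reporting comparator-lens complaints to the manufacturer break the investigator's mask, and does Exclusion 14 let in previous comparator wearers?

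*Protocol*

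**What the plan says.** **Complaint routing.** The last paragraph of Protocol Section 7.5 reads: "The investigator should also report complaints on non-Alcon products directly to the manufacturer", following the manufacturer's instructions or local rules. The paragraph before it deals with data received up to 1 month after a subject leaves the study, and then states: "All complaints received after this time period will be considered and processed as spontaneous". The synopsis gives the comparator's maker as "Johnson & Johnson"; the test lens is made by the sponsor.

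**Masking.** Section 8.1 masks the investigator and most sponsor personnel who handle clinical evaluations, and adds: "Unmasking will occur only after all planned study data have been validated, and the database locked". The exempt sponsor roles are listed: "other than site monitors, clinical operations lead, person responsible for generating the randomization schedule, and unmasked clinical data managers". Section 8.2 gives the investigator one route to the code: "In the event of a medical emergency where the knowledge of subject treatment is required". Section 4.1 (Usage) refers to unmasked staff and makes them responsible for keeping the subject and investigator masked.

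**In-study reporting.** Section 7.3 says that "the investigator must document all device deficiencies reported or observed with test and comparator products on the Device Deficiency eCRF". Device effects and serious events go to the sponsor by eCRF in the same way.

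**Eligibility.** The Study Population row of the synopsis and SAP Table 1-1 both exclude habitual AOHP wearers, current or previous. Exclusion 14 names habitual AOHP wearers with no time qualifier and attaches *current* only to daily disposable wearers.

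**The concern.** Three products are named for use: the test lens, the comparator lens and the care solution. The solution is supplied by the sponsor and has its own route in Section 7.3. For a study lens, the Section 7.5 duty therefore applies only to the comparator, and a masked investigator cannot know whether it applies without learning the lens. With only two sequences, learning the lens in one period also reveals the other. Complaint routing is not an unmasking reason in Section 8.2, and Section 7.5 names no unmasked person for the task. The investigator judges the causality of every adverse event, so a broken mask could colour those judgements.

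On eligibility, Section 3.4 tells sites to screen against the numbered criteria. If *habitual* means the lens worn now, as it does in Inclusion 6 and in the Visit 1 habitual-lens row, a site could enrol a previous AOHP wearer whom the population statement excludes. The visible baseline summaries (Protocol 6.3, SAP Section 3) describe habitual lenses only, so such a subject would not stand out. The documents give no reason for excluding previous wearers. One plausible reason is that they might recognise the comparator.

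**Working it through.** There is no planned figure to reproduce: Protocol 6.10 and SAP Section 7 say that no sample size was calculated. The check is a comparison of passages.

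**1. When would the Section 7.5 duty arise?**
- A torn, defective or contaminated lens during the study is a device deficiency (Section 7.1). Section 7.3 has the investigator record it on the eCRF within 24 hours, for either lens. That step needs no lens identity.
- Device effects and serious events take a parallel eCRF route on the same timetable.
- The Section 7.5 sentence comes directly after the rule for complaints received more than 1 month after exit and is joined to it by *also*. Read in place, it mainly concerns complaints arriving once the subject's visits are over.

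**2. Who would carry it out?**
- Section 4.1 has sites procure the comparator, and provides unmasked staff with a duty to protect the investigator's mask.
- Section 8.1 lists unmasked sponsor roles.
- Nothing visible says that the investigator may be told the lens in order to file a complaint, and Sections 8.1 and 8.2 point the other way. A site that follows all these sections together would pass the task to someone already unmasked.

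**3. What could reach the results if the mask did fail?**
- The SAP's incidence tables (5.3.1) count all ocular and all nonocular treatment-emergent events, whatever their causality.
- Causality enters the visible reporting mainly through significant nonserious events, whose general definition requires a device relation and which Protocol 6.8 says will be identified.
- Under Section 7.3 the sponsor also assesses causality and may upgrade the investigator's judgement.
- Visual acuity with study lenses is measured at Visits 2 to 7, which is 6 visits, of which Visits 3 and 6 (2 visits) supply the primary endpoint. Counting visits left after a disclosure does not give a useful bound. A deficiency can be recorded at Visit 2, for example a lens torn in its pack, and could come before that visit's acuity test: all 6 acuity visits and both primary visits remain. A complaint after exit leaves 0 and 0. The same range holds in both sequences, because deciding that a complaint is *not* about a non-Alcon lens also identifies the lens. A range of 0 to 6 of 6, and 0 to 2 of 2, says nothing about bias.

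**4. Exclusion 14 against the population statement.**

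| Text | AOHP wearers | Daily disposable wearers |
|---|---|---|
| Synopsis; SAP Table 1-1 | current or previous | no separate time qualifier |
| Exclusion 14 | no time qualifier | current |

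The author of Exclusion 14 put *current* on one limb and left it off the other. The natural reading of that contrast is that the AOHP limb is not confined to current wear, which agrees with the population statement. Both texts are in Protocol Section 1, the section to which 3.4 sends sites.

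**The case for a change.** The strongest reply is that the Section 7.5 sentence stands as its own paragraph, with no time limit and no delegate, and that *also* adds a duty rather than replacing one. Masking ends at database lock, not at subject exit, and Section 7.5 keeps the records of ongoing events open until lock. An investigator could therefore learn a lens while that subject's event record can still be edited. Section 7.4 has a similar weakness: it words returns by manufacturer, while Section 4.2 covers any study lens. For Exclusion 14, *habitual* elsewhere points to the present lens, so two sites could in good faith apply two rules.

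Most of this stands as a description of the text. The duty is unassigned, the post-exit reading does not remove every overlap with open records, and the adjective is ambiguous. What does not follow is a breach. Unmasking is possible only if a site overlooks the masking duties in 4.1, 8.1 and 8.2 and gives the code to the one person who must not have it. The Manual of Procedures and a blacked-out part of Section 4.1 cannot be seen; their absence here is not evidence of a gap. The same caution applies to eligibility, where text after the population sentence is redacted.

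**Conclusion.** No change to the plan follows. The first point is an unnamed delegate, a gap that site staff can fill sensibly from roles the protocol already has. The second is a loose adjective that can be read in line with the population stated in both documents; it is a matter of clerical consistency.

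The size of any effect is unknown and cannot be derived, since the documents give no complaint rate and no share of previous AOHP wearers. The consequences are limited by the design: Protocol 6.4.1.1 rules out inference on the primary endpoint, the SAP sets no success criteria, and the adverse event incidence tables do not depend on causality. No estimate, table or conclusion is shown to be wrong if the plan is followed as written.

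This rests on two assumptions: that unmasked staff handle any routing that depends on the manufacturer until database lock, and that sites read Exclusion 14 together with the Study Population row beside it in Section 1. Both are the ordinary reading of the documents.
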